4. LIST OF ABBREVIATIONS

ICH	International Conference on Harmonization
IMOS	Integrated Medical Outcome Scale
ITT	Intent-To-Treat Exposed Population
IWRS	Interactive Web Response System
GCP	Good Clinical Practice
GMP	Good Manufacturing Practice
MEDDRA	Medical Dictionary for Regulatory Activities
PP	population of patients who completed the study protocol
CI	Confidence interval
DNA	Deoxyribonucleic acid
GIT	Gastrointestinal tract
BMI	Body Mass Index
SP	Study product
CRF	Case Report Form
CRO	Contract study organization
MP	Medicinal product
ICD	International Statistical Classification of Diseases
INR	International normalization ratio
LLC	Limited Liability Company
ARVI	acute respiratory viral infection
NPO	Scientific Production Association
AE/SAE	adverse event/serious adverse event
AR	adverse reaction
SOP	standard operating procedure
ESR	Erythrocyte sedimentation rate
COX	Cyclooxygenase
RR	Respiration rate
HR	Heart rate
ECG	Electrocardiogram

5. STUDY RATIONALE

5.1. Background

Polyoxidonium® is a physiologically active compound with a molecular mass of 60 to 100 kDa, which has a pronounced immunomodulating activity [1]. Polyoxidonium® belongs to a class of water-soluble derivatives of hetero-chain aliphatic polyamines. There is no analogues with a similar structure and characteristics in the world for this class of compounds [2]. Since 1983 the mechanism of action of Polyoxidonium® on all immune system components have been studied in detail by a group of authors led by R.V. Petrova [3]. It was established that this drug influences activation of nonspecific resistance of the body, phagocytosis, humoral and cellular immunity. One of the key biological properties of Polyoxidonium® is an ability to stimulate the anti-infective resistance of the body.

Previous experience showed that a majority of secondary immunodeficiency states, presenting in chronic, recurrent or indolent infectious and inflammatory diseases (skin and soft tissues, eyes, bronchopulmonary apparatus, gastrointestinal, urogenital), as well as acute bacterial and viral infections, may be treated with Polyoxidonium® (as part of complex treatment). Numerous clinical studies have proven its high efficacy and safety, dosage and treatment regimens have been developed for various diseases.

The Sponsor company "NPO Petrovax Pharm LLC", Russia, is planning to register a new dosage form of Polyoxidonium® in Russian Federation - nasal and sublingual spray for use in children aged 1 to 12 years -.

5.2. Name and description of the study products

The efficacy of Polyoxidonium®, nasal and sublingual spray, 6 mg/ml (NPO Petrovax Pharm, LLC, Russia) in comparison with placebo for complex therapy of children aged 1 to 12 years with ARVI will be evaluated in this study. The hypothesis of the study product superiority over placebo will be used for efficacy assessment.

Study product - Polyoxidonium®, nasal and sublingual spray, 6 mg/ml (NPO Petrovax Pharm, LLC, Russia).

Comparator - Placebo, nasal and sublingual spray, (NPO Petrovax Pharm, LLC, Russia) - similar to the study product, having an identical presentation, composition of excipients and appearance, but devoid of the active ingredient.

Below you can see basic information on the test product and the comparator relevant to this study.

5.2.1 Study product

Trade name: Polyoxidonium®

International non-proprietary name: Azoximer bromide

Pharmaceutical form: Nasal and sublingual spray.

Composition per 1 ml:

Component	Amount, mg
Active ingredient:	
Azoximer bromide	6.0
Auxiliary substances:	
Mannitol	1.8
Povidone K 17	1.2
Purified water	Up to 1.0

Appearance: clear, colorless or pale yellow solution.

Pharmacotherapeutic group: immunomodulating agent.

ATC: Immune potentiators.

ATC code: [L03]

Pharmacological effect:

Pharmacodynamics

Azoximer bromide has a complex action: immunomodulating, detoxifying, antioxidant, moderate anti-inflammatory.

The basis of The mechanism of immunomodulatory action of Azoximer bromide is based on a direct effect on phagocytic cells and natural killers, and also on stimulation of antibody formation and synthesis of interferon alpha and interferon gamma. Detoxification and antioxidant properties of Azoximer bromide are largely determined by the structure and high molecular weight of the drug. Azoximer bromide increases the body's resistance to local and generalized infections caused by bacteria, fungi, viruses. It restores immunity in secondary immunodeficiency states caused by various infections.

A characteristic feature of Azoximer bromide with topical (intranasal, sublingual) administration is the ability to activate early defense factors of the body against infection: the drug stimulates bactericidal properties of neutrophils, macrophages, enhances their ability to absorb bacteria, increases the bactericidal properties of saliva and the secretion of mucosa of the upper respiratory tract.

Azoximer bromide is well tolerated, does not have mitogenic, polyclonal activity, antigenic properties, it also does not have allergic, mutagenic, embryotoxic, teratogenic and carcinogenic effects. Azoximer bromide has no smell or taste, does not have a local irritant effect when applied on the mucosa of the nose and oropharynx.

Pharmacokinetics

Indications for use

It is used in adults and children from 1 year:

- For treatment of influenza and other ARVIs (at any moment from the onset of disease and during recuperation period);
- For prevention of influenza and other ARVIs (within 1 month before the expected seasonal increase in incidence);
- As part of complex therapy for treatment of acute bacterial and fungal infections of ENT organs (acute and chronic rhinitis, rhinosinusitis, adenoiditis);
- As part of complex therapy to prevent complications and recurrence of chronic ENT organ diseases (including tonsillitis, otitis, sinusitis);
- As part of complex therapy for acute and chronic allergic diseases (including pollinosis, allergic rhinitis) complicated by a bacterial, viral or fungal infection;
- For preoperative preparation of patients before surgical interventions on ENT organs, and also during postoperative period to prevent infectious complications and relapses of the disease.
- As part of complex therapy to enhance the regenerative processes of ENT organ mucosae after acute viral, bacterial and fungal infections;

Contraindications

- Increased individual sensitivity;
- Pregnancy, lactation;
- Children younger than 1 years old;

- Acute renal failure.

With caution

- chronic renal failure (used no more frequently than 2 times a week).

Posology and Administration

Polyoxidonium[®] route of administration: intranasal, sublingual.

Dose regimen, route of administration, the need and the frequency of subsequent therapy are chosen by the physician depending on the disease severity and the age of the patient.

Posology and administration in adults and children older than 12 years.

The drug is administered intranasal or in the sublingual area for 7-10 days at a daily dose of 6 mg:

Intranasal	In the sublingual region
1 spray into each nostril - 5 times a day	2 sprays - 5 times a day

Posology and administration in children aged 1 to 12 years.

The drug is administered intranasal or in the sublingual area for 7-10 days at a daily dose of 0.15 mg/kg:

Age	Intranasal	In the sublingual region
Aged 1 to 2 years	1 spray into each nostril - 1 time a day	1 spray - 2 times a day
Aged 2 to 5 years	1 spray into each nostril - 2 times a day	2 sprays - 2 times a day
Aged 5 to 8 years	1 spray into each nostril - 3 times a day	2 sprays - 3 times a day
Aged 8 to 12 years	2 sprays into each nostril - 2 times a day	4 sprays - 2 times a day

Side effects:

- An allergic reaction may develop in case of increased individual sensitivity to the product components.
- Possible body temperature elevation.

Overdose

No cases of overdose are recorded.

Interaction with other drugs

No drug–drug interactions have been identified.

Special warnings

If an allergic reaction is developed, immediately discontinue the use of Polyoxidonium® and consult a physician.

If the administration of a due dose is missed, the drug should subsequently be administered normally, as indicated in the prescribing information or recommended by the physician. Do not administer a double dose to compensate missed doses.

Do not use the drug in the presence of visual signs of its unsuitability (package defect, change in the product color).

Effect on the ability to operate vehicles and mechanisms

The use of Polyoxidonium® does not affect the ability to perform potentially dangerous activities requiring increased concentration of attention and speed of psychomotor reactions (including driving, working with moving mechanisms).

Presentation: Nasal and sublingual spray.

Per 10 ml in a dark glass vial. 1 vial with a sprayer and the Patient information leaflet in a carton.

Storage conditions: Store in the closed manufacturer's package away from direct sunlight, at 2 - 8 °C. Keep out of reach of children.

Shelf life: 2 years. Do not use after the expiration date.

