	
Suspicion on initial manifestations of diseases with symptoms similar to ARVI signs (other infectious diseases, flu-like syndrome at the debut of systemic connective tissue diseases and other pathology).
 
Positive express test for influenza or streptococcal infection.
 
Clinical symptoms of severe ARVI requiring hospitalization (fever $\geq 40^{\circ}\text{C}$, signs of respiratory obstruction, severe hemodynamic/neurological disorders).
 
A history of or previously diagnosed primary and secondary immunodeficiency.
 
Cancer.
 
Acute infectious or non-infectious diseases (except for ARVI), as well as exacerbation or decompensation of chronic diseases (diabetes mellitus, infantile cerebral palsy, cystic fibrosis, primary ciliary dyskinesia, bronchopulmonary dysplasia, respiratory and ENT organ malformations, etc.) affecting the patient's ability to participate in a study.
 
Sucrase/isomaltase deficiency, fructose intolerance, glucose-galactose malabsorption.
 
A history of allergy/hypersensitivity to any component of products used in treatment (including sensitivity to paracetamol, propacetamol hydrochloride (paracetamol prodrug)).
 
Use of drugs specified in Forbidden Therapy for 1 month prior to study entry.
 
Patients whose parents/adoptive parents may fail to follow the observation requirements during the study or observe the mode of study product administration, in investigator's opinion.
 
Participation in other studies of medicinal products within 3 months to screening visit.
 
Pregnancy.
 
Any other medical or social condition that may interrupt patient's study participation, investigator's opinion.

Exclusion criteria:	
inability or refusal of the patient or his parents/adoptive parents to follow the Protocol's requirements.
 
Informed Consent withdrawal by the patient or his/her parent/adoptive parent.
 
Requirement for additional therapy which is not permitted under this Protocol.

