7.4 Use of the study products. Description and labeling

All study products will be supplied with Certificates of Analysis. Packaging and labeling will be carried out in accordance with the legislation of the Russian Federation on medicinal products and the requirements of Good Manufacturing Practice (GMP). Labels will be made in Russian separately for primary and secondary packaging and contain the following information:

Name of the product: Polyoxidonium[®]/Placebo

Nasal and sublingual spray

Dose number per pack

Protocol code

Randomization patient's ID

Pack or vial No.

Storage conditions

Sponsor's name and address

Study Center No.

Full name of the Principal Investigator:

Product batch and shelf life

Inscription: "For clinical trial use only"

Additionally, the name "N" or "X" will be indicated on the primary and secondary package of study products/placebo.

The Sponsor will pre-label the study products and transfer it to the Clinical Centers.

Study product/placebo dose method:

When using a study product/placebo, the study physicians shall follow the instructions provided below. On Visit 1 (Visit 0, if it is combined with Visit 1) in the Clinical Center conditions/at home, the first administration of SP/placebo (depending on the group) in the sublingual area/nasal passages will be performed to the patient. At the same time, a parent/adoptive parent will also be trained to use the study products by himself/herself at home.

First administration of the SP/placebo is performed on Visit 1 (or Visit 0, if it is combined with Visit 1).

Subsequent administration (if provided) is performed at regular intervals:

12 ± 2 h - with 2-fold administration of the SP/placebo

8 ± 1 h - with 3-fold administration of the SP/placebo

Required dosages of the study product/placebo

Every day, at a daily dose of 0.15 mg/kg for 7 days.

- for children aged 1 to 2 years: 1 spray x 2 times a day, sublingual;
- for children aged 2 to 5 years: 1 spray x 2 times a day, intranasal into each nostril;
- for children aged 5 to 8 years: 1 spray x 3 times a day, intranasal into each nostril;
- for children aged 8 to 12 years: 2 sprays x 2 times a day, intranasal into each nostril.

Use of the concomitant therapy product - Efferalgan®.

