8.1 Inclusion criteria

A patient shall meet the following inclusion criteria:

1. Patients of both sexes aged 1 to 12 years inclusive.
2. Diagnosis of ARVI [ICD-10 code: J00 - Acute nasopharyngitis (runny nose), J02 - Acute pharyngitis, J02.9 - Unspecified acute pharyngitis, Acute laryngitis and tracheitis - J04, J04.0 - Acute laryngitis, J04.1 - Acute tracheitis, J04.2 - Acute laryngitis, Acute upper respiratory tract infections of multiple and unspecified localization - J06, J06.0 - Acute laryngopharyngitis, J06.9 - Acute upper respiratory tract infection, unspecified] confirmed by physician's examination: axillary temperature ≥ 37.0 °C (measured at the moment of physical examination) and Symptom Assessment Scale total score ≥ 5 points, not less than 3 of which should be related to ENT-organs and upper respiratory tract affection (accord. the Symptom Assessment Scale [Appendix 1]).
3. Not more than 24 hours from the onset of ARVI manifestations.
4. Signing an Informed Consent Form by one of the parents/adoptive parent of the child and the child him/herself (if aged ≥ 10 years);

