8.2 Non-inclusion criteria

A patient will not be enrolled, if he/she meets at least one of the following criteria:

1. Suspicion on pneumonia, bacterial infection (including meningitis, sepsis, otitis media, sinusitis, urinary tract infection, etc.) or the presence of a disease requiring the prescription of antibacterial drugs, starting from the first day of the disease.
2. Suspicion on initial manifestations of diseases with symptoms similar to ARVI signs (other infectious diseases, flu-like syndrome at the debut of systemic connective tissue diseases and other pathology).
3. Positive express test for influenza or streptococcal infection.
4. Clinical symptoms of severe ARVI requiring hospitalization (fever ≥ 40 °C, signs of respiratory obstruction, severe hemodynamic/neurological disorders).
5. A history of or previously diagnosed primary and secondary immunodeficiency.
6. Cancer.
7. Acute infectious or non-infectious diseases (except for ARVI), as well as exacerbation or decompensation of chronic diseases (diabetes mellitus, infantile cerebral palsy, cystic fibrosis, primary ciliary dyskinesia, bronchopulmonary dysplasia, respiratory and ENT organ malformations, etc.) affecting the patient's ability to participate in a study.
8. .Sucrase/isomaltase deficiency, fructose intolerance, glucose-galactose malabsorption.
9. A history of allergy/hypersensitivity to any component of products used in treatment (including sensitivity to paracetamol, propacetamol hydrochloride (paracetamol prodrug)).
10. Use of drugs specified in Forbidden Therapy for 1 month prior to study entry.
11. Patients whose parents/adoptive parents, from the point of view of the study, will not fulfill the observation requirements during the study or observe the mode of study product administration.
12. Participation in other clinical studies of medicinal products for less than 3 months to the screening visit.
13. Pregnancy.
14. Any other medical or social condition that, in the opinion of the study physician, prevents the child from this study participation.

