Screening is carried out to determine whether patients comply with the inclusion criteria and do not comply with non-inclusion criteria.

This visit must be held within 24 hours from the onset of the first ARVI symptoms.

Before conducting any screening visit procedures, you must have a signed Informed Consent Form by one of the parents/adoptive parent of the child, as well as the child himself (if the child is ≥ 10 years old) and the Investigator.

In order to determine the patient's compliance with the required inclusion criteria and non-inclusion criteria, it is necessary to conduct a clinical assessment of the patient's health, which will include the following procedures:

- Physical examination, demographic and anthropometric data collection;
- Measurement of major vital signs (HR, RR, body temperature);
- Symptom Assessment Scale completion;
- Express test for influenza;
- Express test for streptococcal infection;
- Complaints and anamnestic data collection: disease duration, effect of the previously received therapy, as well as data on concomitant therapy;
- Clinical blood test;
- Common urine analysis;
- pregnancy test (for female patients with a history of menarche);
- 12-lead ECG (only if there is a suspicion of cardiovascular pathology);
- Assessment of inclusion/exclusion criteria;
- Establishment of a clinical diagnosis;

The Investigator will assess the results obtained to determine the patient's compliance with the required inclusion criteria and non-inclusion criteria. If a patient meets all inclusion criteria, and does not meet any non-inclusion criteria, he/she can be enrolled and admitted to Visit 1 (which can be combined with Visit 0 (Screening)).

9.1.2 Visit 1 (Randomization, Day 1). Therapy period.

Visit 1 (Randomization, Day 1) can be combined with Visit 0 (Screening) held at the clinical center/at home. On Visit 1, the patient's compliance with all inclusion and non-inclusion criteria shall be reassessed. This assessment is carried out through the following procedures.

- Assessment of concomitant therapy

- Collection of patient's complaints
- Physical examination;
- Measurement of vital signs (HR, RR, body temperature)
- Symptom Assessment Scale completion

If the patient meets the requirements of inclusion/non-inclusion criteria, a randomization procedure shall be performed. It can be carried out prior to obtain the laboratory study results. After this, the following actions are performed:

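### Renal failure is restricted in the protocol's product information but named in no eligibility criterion, and the fixed 7-day daily regimen cannot respect the caution

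*Combined protocol and SAP*

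**What the plan says.** Section 5.2.1 (Study product) gives four contraindication lines: individual sensitivity, pregnancy or lactation, age under 1 year, and acute renal failure. Its caution heading has a single entry: "chronic renal failure (used no more frequently than 2 times a week").

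Section 7.4 sets one regimen, varied only by age band: "Every day, at a daily dose of 0.15 mg/kg for 7 days". It offers no reduced schedule.

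Section 8.2 has 14 non-inclusion criteria. Three bear on this point:

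- Criterion 7 covers acute infectious or non-infectious disease other than ARVI, and "exacerbation or decompensation of chronic diseases", where these affect the child's ability to take part. Its examples are open-ended and include no kidney disease.
- Criterion 9 is "A history of allergy/hypersensitivity to any component of products used in treatment".
- Criterion 14 covers any other medical or social condition that, "in the opinion of the study physician, prevents the child from this study participation". The synopsis has its own version, beginning "Any other medical or social condition that may interrupt".

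Renal failure appears in neither list. Inclusion criterion 1 in section 8.1 sets the age limit: "Patients of both sexes aged 1 to 12 years inclusive".

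**The concern.** Eligibility criteria should carry over the restrictions that the protocol itself places on the product, above all when the regimen cannot be adapted to the individual child. Here most were carried over and the renal ones were not. A child with stable chronic renal failure and a cold therefore meets no specific bar to entry. If allocated to active product, that child would be dosed two or three times a day for a week, against the only caution that section 5.2.1 lists.

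The caution is consistent with the non-clinical data in section 5.3. These report nephrotoxic effects in rats at 10 mg/kg, stated to be 50 times the maximum single human dose, and kidney toxicity at very high intraperitoneal doses. Those exposures are far above trial dosing and do not show that harm would occur here. What is at stake is the safety of a possible few children in a placebo-controlled trial of a self-limiting illness.

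**Working it through.** **Contraindications against eligibility criteria.**

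| Restriction in 5.2.1 | Named counterpart |
|---|---|
| Individual sensitivity | 8.2, criterion 9 |
| Pregnancy, lactation | 8.2, criterion 13 (lactation not named; immaterial at ages 1 to 12) |
| Age under 1 year | 8.1, criterion 1 |
| Acute renal failure | None; criterion 7 may apply |
| Chronic renal failure (caution) | None; criterion 14 at discretion |

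Three of the four contraindication lines have a named counterpart. Renal failure is named in 0 of the 14 non-inclusion criteria. Criterion 8 even carries over a rare contraindication of the supplied antipyretic: sucrase/isomaltase deficiency and related intolerances, listed in section 9.3.2.

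**Dosing against the cap.** Inputs are the schedules in section 7.4 and the course totals in section 9.4. Applications = times per day × 7. Doses = sprays per application × times per day × 7.

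| Age band | Times per day | Sprays per application | Applications in 7 days | Doses in 7 days |
|---|---|---|---|---|
| 1 to 2 years | 2 | 1 | 14 | 14 |
| 2 to 5 years | 2 | 2 | 14 | 28 |
| 5 to 8 years | 3 | 2 | 21 | 42 |
| 8 to 12 years | 2 | 4 | 14 | 56 |

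These reproduce the totals in section 9.4 exactly. The cap in section 5.2.1 can be read in two ways:

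- As dosing days: 7 / 2 = 3.5 times the cap.
- As applications: 14 / 2 = 7 times, or 21 / 2 = 10.5 times for the 5 to 8 year band.

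The first reading is the conservative one and is used in the conclusion.

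**Can an investigator follow the caution inside the trial?** Section 5.2.1 leaves the regimen to the physician, but section 7.4 fixes it. Sections 9.4 and 13.3 tolerate at most 2 missed applications on a twice-daily schedule and 4 on a three-times-daily schedule. Dosing on only 2 days would miss 14 − 4 = 10 applications, or 21 − 6 = 15. Compliance would be 4/14 = 6/21 = 29%, against the 80% that section 9.4 requires for the efficacy analysis. Following the caution would therefore be a significant deviation, so it has to be respected at entry.

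**Would screening catch the child anyway?** Section 9.1.6 records previous and concurrent diseases, so known renal failure should come to light, but no specific criterion tells the investigator to act on it. Laboratory work is not a dependable safety net. Section 9.1.6 omits blood chemistry, and section 9.1.2 says of randomization: "It can be carried out prior to obtain the laboratory study results". The first dose is given at that same visit.

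**Children on active product.** At 1:1, 172 / 2 = 86. This is the size of the active arm, not the number at risk.

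**The case against.** The best defence is that the protocol already deals with both conditions without naming them. Acute renal failure is an acute non-infectious disease, and a condition that contraindicates the study drug affects a child's ability to take part, so criterion 7 would in practice probably exclude it. Chronic renal failure is a caution, which leaves the decision to a physician, and criterion 14 provides for that decision. The principal investigator must review the protocol and Investigator's Brochure before starting (section 5.6). History is taken at screening, criteria are reassessed at Visit 1, the consent discussion covers contraindications (section 15.4), and section 8.3 allows later withdrawal for any condition that reasonably requires it. A physician who sees that the regimen cannot be reduced has good reason to use criterion 14. Finally, since the remedy relies on history alone, the laboratory schedule says little about whether there is a defect.

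Much of this stands. Acute renal failure is the weaker half of the point, and the laboratory argument shows only that there is no second line of defence. What remains is stable chronic renal failure. Criterion 7 does not reach it, and criterion 14 depends on each physician, across the 13 listed sites, recalling a caution in the product description and judging it disqualifying. The consent discussion is required to cover contraindications; cautions are not mentioned.

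**Conclusion.** The point holds as a minor one. As written, a child with stable chronic renal failure meets no specific non-inclusion criterion and could be dosed on 7 days in a week where the protocol's own product information allows 2. The 3.5-fold figure assumes that the cap counts dosing days. It compares schedules and is not an estimate of harm. The textual omission is certain. How many children it concerns is unknown, because the documents give no prevalence, and the number may be zero. Nothing here touches the efficacy comparison, the sample size, the error rate or bias.

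**What to change.** Add one non-inclusion criterion to section 8.2 and the same line to the synopsis: *known acute or chronic renal failure*. Answer it from the history of previous and concurrent diseases that section 9.1.6 already collects, with no new test or visit. Naming both conditions covers the contraindication and the caution together. Exclusion is simpler than writing a reduced schedule into a fixed, blinded regimen. The cost is one line in two places and a negligible loss of eligible children.
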